## 1.0 INTRODUCTION

On 17 Nov 2006, the U.S. Food and Drug Administration (FDA) approved Mentor's MemoryGel® silicone gel-filled breast implants for use in women who are undergoing primary or revisional breast augmentation and primary or revisional breast reconstruction surgery. The approval was conditional on Mentor conducting a 10-year study designed to collect long-term experience in U.S. women with MemoryGel implants. The MemoryGel Postapproval Study (MemoryGel PAS) is intended to satisfy one element of FDA's postapproval requirements.

As a condition to gaining access to MemoryGel products, physicians were required to sign up for the MemoryGel Gel-Filled Breast implants Post Approval study, and were asked to actively encourage 41,900 women to participate in the 10-year study. In addition, the study included 1,000 women who were undergoing breast implantation with saline breast implants to serve as concurrent controls for assessing rheumatologic and neurologic signs and symptoms.

Approximately 1,700 centers participated in the study and enrollment included 41,451 MemoryGel participants and 1039 saline participants. Study enrollment has been closed since 15 Oct 2008. As of the last annual study report (dated Nov 2013), the follow-up rates through six years were 21.8% for MemoryGel participants and 15.0% for saline participants.

Due in part to the low follow-up rate, which may limit interpretation of the data, FDA in collaboration with the American Society of Plastic Surgeons (ASPS), breast implant manufacturers, and patient representatives have been investigating innovative approaches to collect long-term data on silicone gel breast implants. As part of these efforts, recently, FDA has agreed to changes in the postapproval commitments for the MemoryGel silicone gel-filled breast implants that include changes to MemoryGel PAS. These changes are described in this amended protocol.

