### 3.0 DESIGN

This protocol amendment includes participant follow-up only. Study enrollment has been closed since 15 Oct 2008 and no new study participants will be enrolled. Data collection will only take place if a participant requires a secondary procedure/reoperation. There are no longer requirements for scheduled office visits or annual participant questionnaires. The study is currently in year 7 and follow-up will continue through 10 years or until the National Breast Implant Registry opens for data collection, whichever occurs first.

As in the original protocol, there will be no concurrent controls needed as a source of comparison for secondary procedures/reoperations (see local complications category in original study design Tables 1 and 2). Thus, saline implant participants will not have data collected under this amended protocol.

Mentor will employ third party study entities that will be responsible for the following: (1) collecting data from surgeons; (2) entering data into and administering the study database; (3) generating follow-up reports as well as datasets; (4) meeting with Mentor on a regular basis; and (5) analyzing the study data. Mentor will be responsible for: (1) IRB approval; (2) monitoring third party entities; (3) analyzing the study data; and (4) periodic reporting to FDA.

The postapproval study was originally designed as follows:

*MemoryGel™ PAS uses a current cohort design of the first 41,900 women receiving Mentor's MemoryGel implants, with 10 years of follow-up. It will include augmentation, reconstruction, and revision patients, each in their naturally occurring proportions at participating study sites.*

*For the purpose of assessing rheumatological and neurological signs and symptoms, there also will be 1,000 saline breast implant patients from the participating surgeons' practices who will serve as concurrent controls. Concurrent control participants will be enrolled by approximately 30 physicians who routinely use saline implants. These investigative sites will be selected with the objective of obtaining the desired number of controls in an appropriate time frame, e.g. roughly the same time frame as the recruitment of MemoryGel subjects. These sites are to enroll all saline subjects meeting the specified eligibility criteria until 1,000 controls are recruited into this study.*

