**Rheumatological and Neurological Signs and Symptoms**

*In contrast to all of the above analyses, this analysis will be based on both the MemoryGel participants and the concurrent saline controls. The study will collect information on rheumatological and neurological signs and symptoms.*

*For each individual rheumatological and neurological sign and symptom, the rheumatological categories for persistent fatigue, combined pain, and fibromyalgia-like symptoms, and the combined neurological categories for central nervous system-related, peripheral nervous system-related, and muscle-related signs and symptoms, the post-baseline prevalence will be estimated for each participant as the proportion of post-baseline contacts in which the participant reports the sign or symptom to be present at the time of the contact. These proportions will be averaged across MemoryGel participants and averaged across the controls. For all of the above, except the individual signs and symptoms, the proportions for the control participants will be compared to the corresponding proportions for the approximately 10,000 MemoryGel participants with whom they are concurrent. Regression analyses will be used to adjust for differences in age, race, and other relevant patient characteristics. The significance of the difference between the two will be tested for significance using a one-sided test conducted at the 0.05 level of significance. These means will be compared using a test based on the normal approximation. In addition, 95% confidence intervals for the estimated prevalences will be computed.*

*These analyses will be performed for the following rheumatological signs and symptoms categories:*

- *Persistent fatigue*
- *Combined pain*
  - *persistent non-traumatic joint pain (more than 3 months), **OR***
  - *persistent muscle pain (more than 3 months), **OR***
  - *pain in taking a deep breath for more than a few days (pleurisy)*
- *Fibromyalgia-like symptoms*
  - *VAS fatigue scale  $\geq 6$  **AND***
  - *Regional pain scale (RPS)-derived body pain questionnaire  $\geq 8$*

*Additionally, these analyses will be performed for the following combined neurological categories:*

- *Central nervous system (CNS)-related*
  - *persistent memory problems and difficulty concentrating on simple tasks, such as reading or television lasting at least 3 months, **OR***
  - *seizure, convulsion, or fit **OR***
  - *episode of sudden visual loss or double vision, **OR***

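### Saline controls come from about 30 saline-using practices and most of their MemoryGel comparators from other practices; with no practice term, practice differences cannot be separated from an association with implant type.

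*Combined protocol and SAP*

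**What the plan says.** Section 3.0 (Design, text of the original protocol) takes the controls from study practices: "1,000 saline breast implant patients from the participating surgeons' practices who will serve as concurrent controls". It then narrows the source: "Concurrent control participants will be enrolled by approximately 30 physicians who routinely use saline implants". Sites were to be selected so that enough controls were recruited in time, which the section describes as "roughly the same time frame as the recruitment of MemoryGel subjects". Within those sites, intake was complete: "These sites are to enroll all saline subjects meeting the specified eligibility criteria until 1,000 controls are recruited into this study".

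Section 11.1 (Rheumatological and Neurological Signs and Symptoms) compares the controls with "the corresponding proportions for the approximately 10,000 MemoryGel participants with whom they are concurrent". On adjustment it says: "Regression analyses will be used to adjust for differences in age, race, and other relevant patient characteristics". On the test it says: "These means will be compared using a test based on the normal approximation". Neither Section 11.1 nor Section 11.2 restricts the MemoryGel women to control-enrolling practices, stratifies by practice or names a practice term.

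Section 1.0 gives the scale: "Approximately 1,700 centers participated in the study", with 41,451 MemoryGel and 1,039 saline women enrolled. Amendment 2 stops collecting these outcomes. However, Section 11.1 still requires a final report on the Amendment 1 phase, analysed as the original protocol describes, so the comparison remains to be reported.

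**The concern.** Control status is tied to a small set of practices picked for their use of saline. If most comparators were treated elsewhere, the contrast between implants is also a contrast between practices. Region, referral pattern and patient mix that was not measured can differ between the two sets of practices, in either direction. A regression on patient characteristics removes only what those characteristics capture. Allowing for correlation within practices would widen the interval but would not move the estimate.

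At stake is the study's only concurrent control group (Table 2), and so every symptom category tested against it. A raised prevalence among MemoryGel women could partly reflect where they were treated, and a true excess could be hidden for the same reason.

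**Working it through.** **1. The plan's own figure.** Section 11.2 calls 1,000 controls more than sufficient. Its inputs are 2% prevalence in MemoryGel women, ratio 2.0 (so 1% in controls), one-sided 0.05, 80% power, 8 reports per woman and correlation 0.30.
- Variance factor for a woman's mean over m reports: [1 + (m − 1)ρ]/m = (1 + 7 × 0.30)/8 = 0.3875.
- SE for 1,000 controls against 10,000: √{0.3875 × (0.01 × 0.99/1,000 + 0.02 × 0.98/10,000)} = 0.00214.
- Power: Φ(0.01/0.00214 − 1.645) = 99.9%, or 99.4% with a pooled null variance. For 80% power, 249 (unpooled) or 396 (pooled) controls are enough.

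The sufficiency statement therefore reproduces. It simply makes no allowance for practice.

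**2. Where the 10,000 must come from.**
- Women per centre: 41,451/1,700 = 24.4. Thirty average centres: 30 × 41,451/1,700 ≈ 731.
- Even if all 731 were concurrent, they would be 731/10,000 = 7.3% of the comparison set.
- Supplying 10,000 takes 10,000/24.4 ≈ 410 average centres, or 10,000/30 ≈ 333 women at each control site.
- For the control sites to supply even half, each would need 5,000/30 ≈ 167 women, nearly seven times the average.

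**3. Sensitivity of the planned test (illustration only).** The documents give no practice effect, so this shows an assumed range. Suppose there is no implant effect, MemoryGel prevalence is 2%, and control practices report 0.1, 0.2, 0.3 or 0.5 percentage points less. With 1,000 against 10,000 women, the one-sided 5% test rejects 9.8%, 17.9%, 29.8% or 62.5% of the time. A shift of 0.5 points in the other direction cuts power at a true ratio of 2.0 from 99.9% to 62.5%.

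**4. What a within-practice comparison could show.** Power = Φ(0.01/SE − 1.645), with 1,039 controls and SE as in step 1. Inputs that the documents do not give:
- Site size: average, or half of it.
- Concurrency: if control sites recruited at the average pace, the concurrent share is 731 × 10,000/41,451 ≈ 176.
- Fewer reports: 3 contacts with correlation 0.48. For three consecutive annual contacts, two pairs are 1 year apart and one pair is 2 years apart. The midpoints of Section 11.2's ranges give (2 × 0.53 + 0.38)/3 = 0.48. The variance factor is (1 + 2 × 0.48)/3 = 0.653.

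| MemoryGel women at control sites | SE, 8 reports | Power | SE, 3 reports | Power |
|---|---|---|---|---|
| All, average sites: 731 | 0.00375 | 85% | 0.00487 | 66% |
| All, half-size sites: 365 | 0.00495 | 65% | 0.00643 | 46% |
| Concurrent only, average sites: 176 | 0.00684 | 43% | 0.00889 | 30% |

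These figures use enrolled numbers and ignore any loss from stratifying over about 30 practices. Section 4.0 reports follow-up through six years of 21.8% (MemoryGel) and 15.0% (saline), which lowers precision further.

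**The case against.** The other side has several fair points.

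- **The plan does adjust.** The regression covers age, race and an open-ended set of patient characteristics, which could include some markers of region or patient mix. A reader might infer that the groups are linked by calendar time alone; that leaves the regression out. What stands is that no practice term is named and unmeasured differences remain.
- **The plan claims association only.** Section 11.1 says the data cannot establish causality. A reader might infer that practice differences will be reported as an implant effect. The documents do not support that; the difficulty is that the two cannot be separated.
- **All centres is not written.** That the comparators span centres is inferred from the missing site restriction and the arithmetic. The inference fails only if control sites were several times larger than average.
- **The mechanism is limited.** Under Section 3.0, participants themselves report these outcomes by mail, Internet and telephone. Surgeons' habits therefore have no obvious route into the data. Region, referral and patient mix do.
- **A within-practice contrast is no cure.** Selection of implant type by patient remains. For example, saline augmentation is open from age 18 and MemoryGel from 22, and previous silicone implants exclude controls only (Section 4.0). The contrast may also be badly underpowered: 85% holds only if concurrency, the plan's one design link between the groups, is given up.
- **It is late.** Enrolment closed in 2008 and annual reports have been issued, so an analysis added now cannot be called prespecified.

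The last two points limit the remedy. They do not remove the gap.

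**Conclusion.** The point holds as a gap that is cheap to narrow. Practice and implant type are largely confounded in this comparison, and no planned step separates them. The share of comparators from practices without controls is about 93% or more if control sites are of average size (100% − 7.3%), and it remains a majority unless those sites are nearly seven times the average.

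The size and direction of any resulting bias are unknown. The rejection rates in step 3 of the working rest on assumed shifts and are not an estimate of it. The documents do not support concluding that the comparison is biased in a known direction, that 1,000 controls were too few, or that a within-practice analysis would settle the question. Its power ranges from about 85% to about 30% over the assumptions shown, before loss to follow-up beyond the assumed number of reports.

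**What to change.** In Section 11.1 (Rheumatological and Neurological Signs and Symptoms), for the Amendment 1 final report:

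1. Keep the planned comparison with about 10,000 concurrent MemoryGel women.
2. Add a supportive sensitivity analysis, labelled as added later. Restrict the MemoryGel group to women implanted at control-enrolling practices, and enter practice as a stratum or fixed effect in the same regression.
3. State whether it uses only concurrent MemoryGel women or all of them at those practices. Report the actual numbers of practices, MemoryGel women and controls contributing.
4. Present both estimates side by side with confidence intervals, and interpret by comparing them. Say that a non-significant within-practice result does not by itself show that an all-centre difference is due to practice.
5. State as a limitation that the planned comparison cannot separate practice from implant type.

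The cost is one extra model and a short text. Control practices should hold MemoryGel women, because controls come from participating practices (Section 3.0) and surgeons had to join the study to receive MemoryGel (Section 5.0), but the number is not stated. The forms in Section 16.0 carry a site number; I assume the enrolment records do too. The downsides are low precision in the within-practice estimate and patient-level selection between implant types, which this analysis leaves in place.

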**Exclusion Criteria**

A woman is not eligible to enroll in the postapproval study as a saline control participant if she meets any of the following exclusion criteria:

1. Has current or past, unilateral or bilateral, silicone breast implants
2. Has active infection anywhere in her body
3. Has existing breast cancer or pre-cancer of the breast without adequate treatment for those conditions
4. Is currently pregnant or nursing

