#### Complications/Reoperations

The cumulative incidence of key local complications (explantation, and reoperation) for women with MemoryGel implants will be estimated based on physician evaluations for the MemoryGel participants using Kaplan-Meier methodology to estimate the time to the first occurrence of the complication or reoperation. Ninety-five percent confidence intervals will be computed. In addition, the relative frequency of reasons for reoperation will be computed.

Under the original protocol, the purpose of the inclusion of the saline participants was to serve as concurrent controls for assessing rheumatologic and neurologic signs. Rheumatological and neurological data will not be collected under this protocol amendment.

Mentor will generate the following final clinical study reports for submission to FDA:

- One final report at the end of the study phase conducted under Amendment 1, including data from beginning of the study through the end of the study phase under Amendment 1. The statistical analysis will be conducted as described in the original protocol (see below).
- One final report at the end of the study phase conducted under Amendment 2, including data from the execution of Amendment 2 to the end of the study. The statistical analysis will be conducted as described above.

The original analyses conducted to address each of the postapproval study's original objectives are identified below and correspond to issues outlined in Table 1:

*It is important to recognize that this study is observational. As a result, data from this study can be used only to establish association, not causality, and data should be evaluated within the context of the broader composite of literature relating to these issues. All of the analyses, except for the analyses of rheumatological and neurological signs and symptoms, will be based on the MemoryGel participants only.*

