#### **CTDs, Fibromyalgia, Cancer, Neurological Diseases and Suicide**

*The incidence of CTDs (by type), fibromyalgia, cancer (by type), neurological disease (by type), and suicide will each be estimated as the ratio of the number of new cases to the number of person-years of exposure (i.e., observed person-years with silicone breast implants) for MemoryGel participants only. Ninety-five percent confidence intervals will be computed. For CTDs, the incidences of scleroderma, lupus, rheumatoid arthritis, Sjögren's Disease, fibromyalgia, and other CTDs will each be estimated. For cancer, the incidences of breast, brain, lung, and other cancers will each be estimated. For neurological diseases, the incidences of MS, myositis, and other neurological diseases will each be*

*estimated. In addition, Mentor will examine the prevalence of depression and anxiety. Ninety-five percent confidence intervals will be computed.*

*The relative risk for women with MemoryGel implants as compared to national norms will be estimated, standardizing for age, race, and other relevant characteristics, when appropriate. The relative risk will be tested for significance based on a one-sided test conducted at the 0.05 level of significance. Ninety-five percent confidence intervals will also be computed. The sources for the comparison data will include Mayes et al. (2003), and may also include, as appropriate, relevant historical controls such as Brinton et al. (2000, 2001a and b, 2004, and 2006), Hennekens et al. (1996), Deapen et al. 1997, Surveillance Epidemiology and End Results (SEER), National Violent Death Reporting System, U.S. Census data (2002), and/or other reliable and relevant sources, including new sources that may become available during the course of this study. The sources for the comparison data for fibromyalgia will include Brinton et al. 2004, the saline control participants, and/or other reliable and relevant sources, including new sources that may become available during the course of this study.*

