*The baseline questionnaire, as well as the follow-up questionnaire, includes recommendations to all participants to see a rheumatologist or neurologist when the participant indicates she is experiencing certain combinations of signs and symptoms. At baseline, a participant will be advised to see a rheumatologist or neurologist if she identifies certain trigger signs and symptoms as specified in the questionnaire. If a participant does not choose to wait until her specialist evaluation before receiving implants, like all participants, she will be followed for the duration of the study, regardless of what the finding is.*

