## 11.2 Sample Size Determination

Study enrollment has been closed since 15 Oct 2008 and no new study participants will be enrolled.

The sample size for the postapproval study originally was determined in the following manner:

*It is assumed that it is required to have 80% power to be able to detect as statistically significant a relative risk of 2.0 for adverse events that occur, without implants, with a frequency of 2.85 per 100,000. This figure is based on the incidence of scleroderma as reported by Mayes et al. (2003). It is assumed this would be based on a one-sided test conducted at the  $\alpha = 0.05$  level of significance. Based on these specifications, it was determined that approximately 338,000 person-years would be required.*

*Patients are to be followed for 10 years. For purposes of sample size calculation, assuming a follow-up rate of 65% at 10 years and a linear loss to follow-up, there would be an average of 8.075 person-years per participant. Thus, in order to obtain the 338,000 person-years, a total of 41,900 MemoryGel participants would be required.*

*The concurrent control sample size was selected in order to be able to detect a relative risk of 2.0 for MemoryGel participants as compared to control participants, for rheumatologic and neurologic signs and symptoms with a prevalence of approximately 2% among MemoryGel participants. It is assumed this would be based on a one-sided test conducted at the 0.05 level of significance with a power of 80%. Similar combined rheumatologic categories of signs and symptoms from Mentor's existing Core Study of these silicone gel implants all have estimated prevalence of at least 2% after year 2. These data will be analyzed by first computing, for each participant, the proportion of time points in which the participant reports the sign or symptom as being prevalent and then calculating the mean of these participant-level proportions across participants within each group. For purposes of sample size calculation, it is assumed that these means will be compared using a simple test based on the normal approximation.*

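### The MemoryGel-versus-saline symptom comparison is open to baseline confounding: symptoms present before surgery count like new ones, baseline symptom status is not a required covariate, and the tested difference (adjusted or raw) is unclear

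*Combined protocol and SAP*

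**What the plan says.** The comparison is under Rheumatological and Neurological Signs and Symptoms in section 11.1. For each woman the outcome is "the proportion of post-baseline contacts in which the participant reports the sign or symptom to be present at the time of the contact". These proportions are averaged within each group. For six combined categories (three rheumatological, three neurological), the saline average is compared with that of about 10,000 concurrent MemoryGel women.

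On adjustment the section says: "Regression analyses will be used to adjust for differences in age, race, and other relevant patient characteristics". It then calls for a one-sided 0.05 test of the difference, and adds that the means are compared by a normal-approximation test.

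Elsewhere in section 11.1, under CTDs, Fibromyalgia, Cancer, Neurological Diseases and Suicide:
- At baseline a woman is advised to see a specialist "if she identifies certain trigger signs and symptoms as specified in the questionnaire".
- If she goes ahead with implants without waiting for that evaluation, "she will be followed for the duration of the study, regardless of what the finding is".
- Disease incidence, by contrast, is "the ratio of the number of new cases to the number of person-years of exposure".

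Section 4.0 bars a saline control who "Has current or past, unilateral or bilateral, silicone breast implants". The MemoryGel list has no such exclusion and admits revision patients.

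Amendment 2 stops collecting symptom data. The Complications/Reoperations part of section 11.1 nevertheless keeps the original analyses for the final report on the Amendment 1 phase.

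**The concern.** A prevalence counts existing symptoms along with new ones, and that is a legitimate way to describe one group. The difficulty comes when two prevalences are tested against each other in groups that were recruited separately and under different entry rules. Symptoms persist: section 11.2 reports correlations of 0.47 to 0.59 between time points one year apart. Part of any difference present before surgery will therefore reappear in the post-baseline proportions.

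Baseline status of the same symptom is the most direct covariate for this problem, and the trial holds at least some of it. The plan names only age and race and leaves the rest open. The saline controls were enrolled for this comparison, so the report should let a reader separate a pre-surgery difference from a later one. As written, it need not.

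**Working it through.** **The plan's own figure.** Section 11.2 calls 1,000 controls more than sufficient. Inputs from 11.1 and 11.2: 2% MemoryGel prevalence, relative risk 2.0 (so 1% saline), one-sided 0.05, 80% power, 8 reports per woman, average correlation at most 0.30, and 10,000 to 1,000 allocation.
- Variance factor: (1 + 7 × 0.30)/8 = 0.3875.
- Controls needed: (1.645 + 0.842)² × 0.3875 × [0.01 × 0.99 + 0.02 × 0.98/10]/0.01² = about 284.

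The statement holds. The issue is bias, not sample size.

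**Assumptions for the illustration.** The documents give neither a baseline imbalance nor a baseline-to-follow-up correlation (rho). Assumed: baseline prevalence 3% MemoryGel and 2% saline (d = 1 point), no implant effect, and rho from 0.15 to 0.30. The upper value is the plan's ceiling for the average correlation between time points.

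**How far prior symptoms carry over.** With 2% prevalence at baseline and afterwards, the share of symptom-positive later contacts from women already positive at baseline is 0.02 + rho × 0.98. At rho 0.30 this is 0.314, or about 31%.

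**Model A: the imbalance acts only through baseline status.**
- Spurious difference: rho × d = 0.15 to 0.30 points.
- Standard error: sqrt(0.3875 × 0.0196 × (1/10,000 + 1/1,000)) = 0.00289.
- Error: P(Z > 1.645 − rho × 0.01/0.00289) = 13.0%, 17.0% and 27.2% at rho 0.15, 0.20 and 0.30.
- With the imbalance reversed, at rho 0.30: P(Z > 1.645 + 1.038) = about 0.4%, so a real effect could be masked.
- Simulation (beta-binomial, 8 reports, robust standard errors): 15%, 20% and 27% unadjusted; 7%, 8% and 7% with baseline status in the regression.
- Adjustment removes the bias here, but the error does not return to 5%. With no imbalance at all the unadjusted test already rejects 6-7%, because the outcome is rare and skewed.

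**Model B: baseline is one noisy reading of a stable trait.**
- The raw difference is the full 1.0 point.
- The within-group slope on baseline is rho, so the adjusted difference is d × (1 − rho) = 0.85, 0.80 and 0.70 points.
- Simulated rejection at rho 0.30 falls only from 94% to 84%.

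**Change from baseline** (post-baseline proportion minus baseline status).
- It errs the other way: about 0 under B, and −(1 − rho) × d = −0.85 to −0.70 points under A.
- Its standard error at rho 0.30 is sqrt((0.3875 + 1 − 0.60)/0.3875) = 1.43 times that of the raw comparison.

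**Number of reports.** Eight is the plan's ten-year average, but section 3.0 puts the study in year 7. With 7 reports the factor is (1 + 6 × 0.30)/7 = 0.40 and the standard error 0.00294. The Model A error at rho 0.30 is then still about 27%.

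**The case against.** **The open phrase already covers baseline status.** It allows it, and the plan cannot be said to rule it out. A reader might infer that baseline symptoms are left out of the model; the text supports only that they are not required. With a one-sided test and results already reported through six years, the choice should be closed in writing.

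**Prevalence is the chosen measure.** This stands. Counting existing symptoms follows from it and is not an error in itself, and one item (difficulty walking) is even worded as new. What remains is the between-group test.

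**The adjusted difference is surely the one tested.** A reader might infer this from section 11.2, which says: "For purposes of sample size calculation, it is assumed that these means will be compared using a simple test based on the normal approximation". That would confine the simple test to planning. But the analysis section itself also says that the means are compared by normal approximation, straight after calling for regression. Section 11.2 does not settle the matter.

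**No imbalance is shown.** This stands. The differing prior-silicone rules are a reason to look; they do not show that symptoms differed before surgery, nor in which direction.

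**Adjustment may achieve little.** Under Model B that is largely right, so the fix cannot rest on adjustment alone.

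**Conclusion.** The concern holds as a weakness of the between-group test. Three things rest on the text: prior symptoms count like new ones, baseline status is permitted but not required, and the tested difference is ambiguous. The size rests on assumptions. For a 1-point imbalance at the planned group sizes, the nominal 5% error becomes about 13-27% under Model A, and adjustment brings it to about 7-8%. Under Model B, adjustment leaves 0.70-0.85 of the 1.0-point bias.

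A reader might infer that the comparison is biased in a known direction, or that baseline adjustment cures it. The documents support neither. They give no baseline prevalence by group, and adjustment removes only about rho times the imbalance. Nor do these error rates describe the women actually retained: the number contributing reports to this comparison, and how many reports each gave, are not stated.

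This should be changed before the Amendment 1 report is analysed. It does not call for a different sample size.

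**What to change.** For the Amendment 1 report:
1. Make the primary comparison a regression of the participant-level post-baseline proportion on group, baseline status of the same category (where the baseline questionnaire records it), age, race, indication, and primary versus revision surgery, with robust variance.
2. State that the one-sided 0.05 test is of this adjusted group coefficient.
3. Tabulate baseline prevalence of each category by group.
4. Show as sensitivity analyses the unadjusted result, a primary-surgery-only analysis, and a change-from-baseline comparison.
5. If the adjusted and change-from-baseline results disagree, say that baseline confounding is unresolved.

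The cost is analysis text, with no new data collection. The downsides are:
- The baseline questionnaire is not in the documents. Availability for all six categories must be confirmed, and a rule for missing items set. Section 5.0 suggests that operative details were not recorded for controls, so indication and revision status must be confirmed for them too.
- The change comes after six-year results were reported and must be documented as late.
- Adjustment reduces the bias but need not remove it. Change from baseline needs the same item at both times, is less precise, and over-corrects under Model A.
- In revision patients baseline symptoms may reflect earlier silicone, so adjustment may remove part of an effect of that exposure. This is the reason for the primary-surgery-only analysis.
- It does not address attrition (six-year follow-up of 21.8% and 15.0%) or the roughness of the normal approximation for a rare outcome.
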